14.34 Shipping

Specimens must be shipped the same day they are drawn.

Ship in their respective Styrofoam boxes; a cold pack is required. Avoid freezing of specimens. The Fed Ex airbill is pre-addressed.

Ship specimens via Priority Overnight service on **Monday – Thursday Preferred** (Friday only if you must) directly to:

Please email [redacted] or call [redacted] to notify the laboratory when specimens are being shipped. The message should include the study name, sample type, Fed Ex airbill tracking number, contact name and telephone number.

Shipping costs will be covered by the study if these kits and Fed Ex airbills are used for shipping specimens. Each kit contains the required tubes.

15.0 Drug Information

15.1 Lenalidomide (Revlimid®, CC-5013, CDC-501)

Please consult the most current Investigator's Brochure and package insert for complete drug information.

15.11 **Background:** Lenalidomide has a wide range of effects, including the inhibition of hematopoietic tumor cell proliferation, the enhancement of T cells and natural killer (NK) cell activity, the modulation of stem cell differentiation, the inhibition of angiogenesis, and the inhibition of inflammation.

15.12 **Formulation:** For clinical study, lenalidomide is provided as 1.25-, 2.5-, 5-, 10-, 15-, 20-, and 25-mg capsules for oral administration. Each capsule contains lenalidomide as the active ingredient and the following inactive ingredients: anhydrous lactose, microcrystalline cellulose, croscarmellose sodium, and magnesium stearate.

Placebo capsules for the 1.25-, 2.5-, 5-, 10-, 15-, 20-, and 25-mg lenalidomide capsules are available for use in blinded studies. Each placebo capsule visually matches the drug product.

The lenalidomide and placebo capsules are supplied in push-through blister foil or tamper-evident, child-resistant, opaque, high-density polyethylene (HDPE) containers with HDPE caps.

- 15.13 **Preparation and storage:** Lenalidomide should be stored at room temperature, between 59 and 86°F (15-30°C). Store drug away from direct sunlight.
- 15.14 **Administration:** Capsules are administered by mouth daily with water. Patients should not break, chew or open the capsules.
- 15.15 **Pharmacokinetic information:**
- a) Absorption – Lenalidomide is rapidly absorbed following oral administration to subjects with multiple myeloma or MDS, with maximum plasma concentrations occurring between 0.5 and 1.5 hours post-dose. Co-administration with a high-fat and high-calorie meal in healthy subjects reduced the extent of absorption, resulting in an approximately 20% decrease in AUC and 50% decrease in C_{max} in plasma.

In the pivotal MM and MDS registration trials where the efficacy and safety were established for lenalidomide, the drug was administered without regard to food intake. Thus, lenalidomide can be administered with or without food.

Multiple dosing (up to 100 mg BID) did not cause marked drug accumulation.

- b) Distribution – In vitro (^{14}C)-lenalidomide binding to plasma proteins is approximately 30%.
- c) Metabolism – Lenalidomide undergoes limited metabolism. Unchanged lenalidomide is the predominant circulating component in humans. Two identified metabolites are hydroxy-lenalidomide and N-acetyl-lenalidomide; each constitutes less than 5% of parent levels in circulation.
- d) Excretion – Elimination is primarily renal. Approximately 65% to 85% of lenalidomide is eliminated unchanged through urinary excretion in subjects with normal renal function. The half-life of elimination is approximately 3 to 4 hours (2 to 3 hours in patients 5 to 21 years) at the clinically relevant doses (5 to 50 mg/day). Steady-state levels are achieved within 4 days.

- 15.16 **Potential Drug Interactions:** In vitro studies demonstrate that lenalidomide is not a substrate of CYP enzymes. In addition, lenalidomide shows little inhibitory or induction potential towards the CYP enzymes in vitro. Hence, coadministration of CYP substrates, inhibitors, or inducers with lenalidomide is not likely to result in clinically relevant drug-drug interactions in humans.

In vitro, lenalidomide is not a substrate of BCRP, MRP1, MRP2, MRP3, OAT1, OAT3, OATP1B1, OCT1, OCT2, MATE1, OCTN1, or OCTN2. Thus, it is unlikely that substrates or inhibitors of these transporters would affect lenalidomide disposition in humans.

Lenalidomide is not an inhibitor of BSEP, BCRP, MRP2, OAT1, OAT3, OATP1B1, OATP1B3, or OCT2. Thus, lenalidomide is not anticipated to cause any significant drug-drug interactions due to inhibition of these transporters.

Lenalidomide is not an inhibitor of UGT1A1 and is not anticipated to cause any significant drug-drug interactions due to UGT1A1 inhibition.

In vitro, lenalidomide is a weak substrate, but not an inhibitor of P-glycoprotein (P-gp).

Erythropoietic agents or other agents that may increase the risk of thrombosis, such as hormone replacement therapy and oral contraceptives, should be used with caution in patients with multiple myeloma receiving lenalidomide with dexamethasone.

Periodic monitoring of digoxin plasma levels is recommended due to increased C_{max} and AUC with concomitant lenalidomide therapy. Close monitoring of PT and INR is recommended in multiple myeloma patients taking concomitant warfarin.

15.17 **Known potential toxicities:**

Pregnancy Warning: Lenalidomide, a thalidomide analogue, caused limb abnormalities in a developmental monkey study similar to birth defects caused by thalidomide in humans. If lenalidomide is used during pregnancy, a teratogenic effect of lenalidomide in humans cannot be ruled out. Pregnancy must be excluded before start of treatment. Prevent pregnancy during treatment by the use of two reliable methods of contraception.

Very Common AEs ($\geq 10\%$): anemia, leukopenia, neutropenia, thrombocytopenia, cataracts, blurred vision, abdominal pain, constipation, diarrhea, dyspepsia, nausea, vomiting, asthenia, chills, edema including peripheral, fatigue, pyrexia, abnormal liver function tests, bronchitis, nasopharyngitis, pneumonia, rhinitis, upper respiratory tract infection, urinary tract infection weight decreased, decreased appetite, hyperglycemia, hypocalcemia, hypokalemia, arthralgia, back pain, bone pain, muscle spasms, musculoskeletal pain, myalgia, pain in extremity, dizziness, dysgeusia, headache, hypoesthesia, neuropathy peripheral, neuropathy, tremor, depression, insomnia, cough, dyspnea, epistaxis, pharyngitis, pulmonary embolism, dry skin, pruritus, rash, and deep vein thrombosis.

Common ($\geq 1\%$ and $< 10\%$): febrile neutropenia, granulocytopenia, hemolytic anemia, lymphopenia, pancytopenia, acute myocardial infarction, atrial fibrillation, cardiac failure, congestive heart failure, myocardial ischemia, tachycardia, vertigo, upper abdominal pain, dry mouth, , toothache, chest pain, fall, , cholestasis, bacteremia, erysipelas, gastroenteritis, herpes simplex, herpes zoster, influenza, lower respiratory infection, respiratory infection, sinusitis, sepsis, contusion, alanine aminotransferase increased, c-reactive protein increased, gamma-glutamyltransferase increased, dehydration, diabetes mellitus, gout, hyperuricemia, hypophosphatemia, hypomagnesemia, hyponatremia, iron overload, muscular weakness, acute myeloid leukemia, basal cell carcinoma, Myelodysplastic syndrome, squamous cell carcinoma of skin, tumor flare, tumor lysis syndrome, cerebrovascular accident, lethargy, paresthesia, peripheral sensory neuropathy, syncope, mood altered, renal failure, respiratory distress,

erythema, hyperhidrosis, night sweats, hematoma, hypertension, hypotension, peripheral ischemia, thrombosis, and vasculitis.

Uncommon, limited to important or life-threatening (< 1%): hypersensitivity, Graft vs. Host Disease

The following additional adverse reactions have been reported in Celgene-sponsored clinical studies and are considered by the company to be at least possibly related to the administration of lenalidomide: pneumonitis, transient abnormal liver laboratory tests, hyperthyroidism, , TLS, TFR, rhabdomyolysis, and allergic conditions, including angioedema, SJS, and toxic epidermal necrolysis. These reactions are reported voluntarily from a population of uncertain size, so it is not possible to reliably estimate their frequency.

Lenalidomide may have minor or moderate influence on the ability to drive and use machines. Fatigue, dizziness, somnolence, vertigo and blurred vision have been reported with the use of lenalidomide. Therefore, caution is recommended when driving or operating machines.

Please refer to the Investigator's Brochure for a more comprehensive list of treatment-emergent adverse events.

- 15.18 **Drug procurement:** Lenalidomide (Revlimid®) will be provided directly to research subjects for the duration of their participation in this trial at no charge to them or their insurance providers in accordance with the REVLIMID REMS™ program. Per standard requirements all physicians who prescribe lenalidomide for research subjects enrolled into this trial, and all research subjects enrolled into this trial, must be registered in and must comply with all requirements of the Celgene REVLIMID REMS™ program. Prescriptions must be filled within 7 days. **Only enough lenalidomide for one cycle of therapy will be supplied to the patient each cycle.**

Any unused lenalidomide should be returned for disposition in accordance with the REVLIMID REMS™ program.

15.19 **Nursing Guidelines:**

15.191 Myelosuppression is dose-dependent and reversible with treatment interruption and/or dose reduction. Monitor CBC w/diff regularly. Instruct patient to report any unusual bruising or bleeding (thrombocytopenia); signs and symptoms of infection (neutropenia); and energy conserving lifestyle (anemia).

15.192 Lenalidomide can have thrombotic adverse events (i.e DVT and PE). Instruct patient to report any limb swelling or pain, and to seek medical attention for shortness of breath or chest pain.

15.193 Because of the potential for birth defects patients should be instructed in effective methods of birth control. Female patients should use 2 forms of birth control during treatment and for 4 weeks after discontinuing

therapy. Males must be instructed to use a latex condom during any sexual contact with a woman of child bearing potential (even if they have had a vasectomy), because it is unknown if lenalidomide is present in semen.

- 15.194 Patients may experience pruritus, rash and dry skin. Because of the rare risk of Steven's Johnson Syndrome, patients should immediately report any rash to their provider.
- 15.195 Drug may cause hyperglycemia. Patients with diabetes or impaired fasting glucose may need to have their glucose levels monitored more closely.
- 15.196 Gastrointestinal side effects (diarrhea, constipation, nausea, dyspepsia, anorexia, etc) are commonly seen. Manage patient symptomatically and monitor for effectiveness.
- 15.197 Patients may experience myalgias, arthralgias, and other generalized pain. Administer analgesics as ordered and monitor for their effectiveness.
- 15.198 Upper respiratory symptoms (nasopharyngitis, cough, epistaxis, etc.) can be seen. Manage symptomatically and monitor for effectiveness.
- 15.199 Agent may cause fatigue, dizziness, vertigo, or blurred vision. Instruct patients to use caution when driving or operating machines.

15.2 Pneumococcal 13-valent Conjugate Vaccine (Prevnar 13®)

- 15.21 **Background:** Pneumococcal 13-valent Conjugate Vaccine (Diphtheria CRM₁₉₇ Protein), is a sterile solution of saccharides of the capsular antigens of *Streptococcus pneumoniae* serotypes 1, 3, 4, 5, 6A, 6B, 7F, 9V, 14, 18C, 19A, 19F and 23F individually linked to non-toxic diphtheria CRM₁₉₇ protein. Each serotype is grown in soy peptone broth.

Potency of the formulated vaccine is determined by quantification of each of the saccharide antigens, and by the saccharide to protein ratios in the individual glycoconjugates.

- 15.22 **Formulation:** Supplied as ready-to-use prefilled syringes (10 x 0.5-mL prefilled syringes per package). Pneumococcal 13-valent Conjugate Vaccine is manufactured as a liquid preparation for intramuscular injection. Each 0.5 mL dose of the vaccine is formulated to contain approximately 2.2 µg of each of *Streptococcus pneumoniae* serotypes 1, 3, 4, 5, 6A, 7F, 9V, 14, 18C, 19A, 19F, 23F saccharides, 4.4 µg of 6B saccharides, 34 µg CRM₁₉₇ carrier protein, 100 µg polysorbate 80, 295 µg succinate buffer and 125 µg aluminum as aluminum phosphate adjuvant.

- 15.23 **Preparation and storage:** Pneumococcal 13-valent Conjugate Vaccine is stored at refrigerated temperatures of 2°C to 8°C (36°F to 46°F) away from freezer compartment. DO NOT FREEZE. Discard if frozen.
- 15.24 **Administration:** Shake vigorously immediately prior to use to obtain a uniform suspension in the vaccine container. The vaccine should not be used if it cannot be resuspended. After shaking, the vaccine is a homogeneous, white suspension. Do not mix the vaccine with other products in the same syringe.
- The dose is 0.5 mL to be given intramuscularly. **Do not inject intravenously**, intradermally or subcutaneously. The vaccine should not be injected in the gluteal area or areas where there may be a major nerve trunk and/or blood vessel. Before injection, the skin at the injection site should be cleansed and prepared with a suitable germicide. After insertion of the needle, aspirate and wait to see if any blood appears in the syringe, which will help avoid inadvertent injection into a blood vessel. If blood appears, withdraw the needle and prepare for a new injection at another site.
- 15.25 **Potential Drug Interactions:** Patients receiving therapy with immunosuppressive agents (large amounts of corticosteroids, antimetabolites, alkylating agents, cytotoxic agents) may not respond optimally to active immunization.
- As with other intramuscular injections, Pneumococcal 13-valent Conjugate Vaccine should be given with caution to patients on anticoagulant therapy.
- See complete prescribing information for information regarding co-administration of Pneumococcal 13-valent Conjugate Vaccine with other vaccines.
- 15.26 **Known potential toxicities:** There is no safety data available in the adult patient population. Please see Prevnar 13® prescribing information for comprehensive toxicity data.
- The following systemic events were noted within 2-3 days of the Pneumococcal 13-valent Conjugate Vaccine injection in pediatric patients: fever, irritability, drowsiness, restless sleep, decreased appetite, vomiting, diarrhea, and urticaria-like rash. The following local reactions occurred within 3 days of immunization pediatric patients: erythema, induration, tenderness and interference with limb movement.
- 15.27 **Drug procurement:** Commercial supplies. Pharmacies or clinics shall obtain supplies from normal commercial supply chain or wholesaler.
- 15.28 **Nursing Guidelines:**
- 15.281 Monitor for injection site reaction. Local reaction is usually seen within 3 days of vaccination, including erythema, induration and tenderness. Treat symptomatically and monitor for signs on infection.

15.282 Patients may experience mild fever. Acetaminophen can be used symptomatically. Monitor for effectiveness.

15.283 Patients may experience “flu-like” symptoms (fever, irritability, decreased appetite, vomiting and diarrhea). Treat symptomatically.

16.0 Statistical Considerations and Methodology

16.1 Overview:

This is a randomized Phase II study designed to compare the response rate of the control arm (Pevnar 13 alone) to the experimental arm (Pevnar 13 plus lenalidomide).

16.11 Primary Endpoint:

The primary endpoint of this trial is the rate of response to the Pevnar 13 vaccine, which will be compared between the two arms. A response will be defined as a four-fold rise from pre-vaccine (day 15) to 28 days after immunization (day 43) for ≥ 2 of the 3 serotypes studied by opsonophagocytic activity (OPA) of antibodies from sera. Throughout Section 16.0, response will be considered synonymous with “success”, unless specified otherwise. All patients meeting the eligibility criteria who have signed a consent form and, received the Pevnar 13 vaccine will be evaluable for response, with the exception of patients who are determined to be a major treatment violation or flag.

16.2 Statistical Design:

16.21 Decision Rule:

It has been shown that CLL patients have poor response to vaccines. In previous studies, responses to the polysaccharide pneumococcal vaccine (Pneumovax) have been remarkably low, with responses ranging from 10-22%.^{13,14} Similar responses are expected with the Pevnar 13 vaccine. The addition of lenalidomide is expected to increase response rates to Pevnar 13 vaccine.

A randomized trial comparing the experimental arm (Pevnar 13 plus lenalidomide) against the control arm (Pevnar 13 alone) will be conducted as described by Rubinstein³⁴. We will enter 26 evaluable patients on each arm of the study using a 1:1 randomization scheme utilizing the Pocock and Simon dynamic allocation procedure³⁵, where patients are stratified based on age (<65 vs. ≥ 65), Rai stage (MBL or 0 vs. I), and previous Pneumovax (yes vs. no). A sample size of 26 patients per arm provides 80% power to detect an improvement in response rate from 10% to 30%, using a one-sided test at a significance level of 0.16 (EAST 6.2).

The z-score will be calculated for testing the null hypothesis that the difference of response rates between the two arms is equal to zero, based on the normal approximation with pooled variance of standardized test statistics.

16.211 Final Decision Rule: The final analysis will take place after all 52 evaluable patients have completed the response evaluation at 43 days.

The response rates will be compared between the two arms using EAST6. If the response rate is higher in the experimental arm, where the z-score is greater than 0.988 (p-value < 0.162), this will be considered sufficient evidence that the experimental arm may be recommended for further testing in subsequent studies. Otherwise, we will conclude that there is not statistical evidence of superiority of the experimental regimen.

16.212 Over Accrual: If more than the target number of patients are accrued, the additional patients will not be used to evaluate the stopping rule or used in any decision making process. Analyses involving over accrued patients are discussed in Section 16.33.

16.22 Sample Size:

The randomized phase II study design to be used is fully described in section 16.21. A maximum of 52 evaluable patients (26 in each arm) will be accrued onto this phase II study unless undue toxicity is encountered. We anticipate accruing an additional 6 patients (3 in each arm) to account for ineligibility, cancellation, major treatment violation, or failure to receive the Prevnar 13vaccine. Maximum projected accrual is 58 patients.

16.23 Accrual Rate and Study Duration:

The anticipated accrual rate is approximately 3-4 patients per month. Therefore, the accrual period for this phase II study is expected to be about 1.5 years. The final analysis can begin approximately 1.75 years after the trial begins, i.e. as soon as the final patient accrued to this trial has completed the response evaluation at 43 days and data entry has been completed.

16.24 Power and Significance Level: Assuming that the responses are binomially distributed in each arm, the operating characteristics of the current design can be tabulated according to various true differences of the proportions, including the probabilities that the experimental regimen is superior to the control regimen.

If the true difference is proportions is	0	0.10	0.20	0.30
Then the probability of declaring that the experimental regimen warrants further studies is....	0.16	0.51	0.80	0.95

16.25 Other Considerations: Toxicity, quality/duration of response, and patterns of treatment failure observed in this study, as well as scientific discoveries or changes in standard care will be taken into account in any decision to terminate the study.

16.3 Analysis Plan: The analysis for this trial will commence at planned time points (see 16.2) and at the time the patients have become evaluable for the primary endpoint. Such a decision will be made by the Statistician and Study Chair, in accord with CCS Standard Operating Procedures, availability of data for secondary endpoints (eg, laboratory correlates), and the level of data maturity. It is anticipated that the earliest date in which

the results will be made available via manuscript, abstract, or presentation format is when last patient has been followed for at least 2 months.

16.31 Primary Endpoint:

16.311 Definition: The primary endpoint of this trial is the rate of response to the Prevnar 13 vaccine, which will be compared between the two arms. A response will be defined as a four-fold rise from pre-vaccine (day 15) to 28 days after immunization (day 43) for ≥ 2 of the 3 serotypes studied by opsonophagocytic activity (OPA) of antibodies from sera. Patients who are not evaluated for the OPA titers at both pre-vaccine (day 15) and day 43 due to a missed blood draw or other reasons will be considered a non-responder. All patients meeting the eligibility criteria who have signed a consent form and received the Prevnar 13 vaccine will be evaluable for response, with the exception of patients who are determined to be a major treatment violation or flagr.

16.312 Estimation: The proportion of successes will be estimated in each arm by the number of successes divided by the total number of evaluable patients. Ninety-five percent confidence intervals for the true success proportion will be calculated in each arm based on the normal approximation. Comparison of response rates between the two treatment groups will be performed using a one-sided z-test (based on normal approximation with pooled variance of standardized test statistics) at significance level 0.16.

16.32 Secondary Endpoints:

16.321 Disease status by physical exam and complete blood counts will be evaluated in each patient. For CLL, each patient will be classified as CCR, CCRi, PR, SD, or PD per Section 11.2 at the time of the 6 week assessment of immune response. The distribution of disease status will be evaluated in each arm and will be summarized descriptively. Patients will be classified as responders (CCR, CCRi, PR) vs. non-responders (SD, PD). For MBL, patients will be classified as Not PD vs. PD. Differences in disease status response will be compared between the two arms using Fisher's exact test.

16.322 Time to treatment for progressive CLL will be defined as the time from the date of registration to the date of initiation of treatment for progressive CLL. The distribution of time to treatment will be estimated in each arm using the method of Kaplan-Meier. Time to treatment will be compared between the two arms using log-rank statistics.

16.323 Adverse Events: All eligible patients that have initiated treatment will be considered evaluable for assessing adverse event rate(s). Platelets and hemoglobin will be graded according to the Grading Scale for Hematologic Adverse Events in CLL Studies in Appendix IV. The maximum grade for each type of adverse event will be recorded for each patient, and frequency tables will be reviewed for each arm to determine

patterns. Additionally, the relationship of the adverse event(s) to the study treatment will be taken into consideration.

16.33 Correlative Analyses:

16.331 Pre-vaccination (day 15) and day 28 post-vaccination OPA GMTs for each serotype (4, 9V, 23F) will be reported in the vaccine and vaccine + lenalidomide groups. The fold-change in OPA GMT from baseline to 28 days post-vaccination will be evaluated for each serotype, where two-sample t-tests will be used to compare GMTs between the vaccine and vaccine + lenalidomide groups.

16.332 Pre-vaccination (day 15) and day 28 post-vaccination *Streptococcus pneumoniae* serotype specific IgG GMTs for each serotype (1, 3, 4, 5, 6B, 7F, 9V, 14, 18C, 19F, 19A, and 23) will be reported in the vaccine and vaccine + lenalidomide groups. The fold-change in quantitative IgG GMT from pre-vaccine (day 15) to 28 days post-vaccination will be evaluated for each serotype, where two-sample t-tests will be used to compare GMTs between the vaccine and vaccine + lenalidomide groups.

16.333 Measures of global immune function including T-cell repertoire, T-cell immune synapse, serum immunoglobulin levels, and absolute numbers of T-cell and NK cells will be evaluated at both baseline and after 6 weeks of low dose lenalidomide. Values over time will be summarized graphically and descriptively. Changes from baseline to 6 weeks will be evaluated using paired t-tests. Two sample t-tests will be used to compare each measure between the vaccine and vaccine + lenalidomide groups.

16.34 Over Accrual: If more than the target number of patients are accrued, the additional patients will not be used to evaluate the stopping rule or used in any decision making processes; however, they will be included in final point estimates and confidence intervals.

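### The z > 0.988 rule has exact one-sided type I error 0.19 at the 10% design control rate, not the tabulated 0.16, and the normal-approximation 95% CIs under-cover at 26 per arm

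*Combined protocol and SAP*

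**What the plan says.** Section 16.21 sets the design: "A sample size of 26 patients per arm provides 80% power to detect an improvement in response rate from 10% to 30"%. The level is one-sided 0.16, with EAST 6.2 named as the software. The test is a z-test on the difference in response rates, using the normal approximation with pooled variance. For the control rate, the same section says that earlier responses to Pneumovax "have been remarkably low, with responses ranging from 10-22"%, and it anticipates much the same for Prevnar 13.

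Section 16.211 recommends the experimental arm for further testing if its response rate is higher, "where the z-score is greater than 0.988 (p-value < 0.162").

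Section 16.22 adds: "The randomized phase II study design to be used is fully described in section 16.21".

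Section 16.24 begins "Assuming that the responses are binomially distributed in each arm, the operating characteristics of the current design can be tabulated", and it indexes its table only by the true difference between the arms. It gives 0.16, 0.51, 0.80 and 0.95 as the probability of declaring the experimental regimen worth further study at differences of 0, 0.10, 0.20 and 0.30. It does not repeat the control rate, and it does not say that the values are approximate.

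Section 16.312 specifies a normal-approximation 95% confidence interval for the response proportion in each arm. Section 16.34 brings over-accrued patients into the final estimates and intervals.

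**The concern.** With 26 patients per arm and a control rate near 10%, about 2.6 control responders are expected. The normal approximation is poor at such counts, and only a limited set of z values can occur near the cut-off. Section 16.24 names a binomial model, so a reader will take its first entry as the real chance of recommending an ineffective regimen. If that entry is only nominal, the false-positive risk is understated.

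Power for a given difference also depends on the control rate. A table indexed by the difference alone can be misapplied elsewhere in the 10-22% range.

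The per-arm intervals are the plan's reported precision for the primary endpoint. If they are too narrow, or collapse when nobody responds, the published result will look more precise than it is.

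**Working it through.** **Inputs.** n = 26 per arm, 10% versus 30%, one-sided 0.16 and control range 10-22% (16.21); cut-off z > 0.988 (16.211); tabulated values (16.24); interval method (16.312). The plan mentions no continuity correction, so none is used. A result of 0 versus 0 responders counts as no success.

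**Step 1: reproduce the table.** With control rate p, difference d and p̄ = p + d/2:

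power = Φ[(d − 0.988·s₀)/s₁], where s₀ = √(2p̄(1−p̄)/26) and s₁ = √([p(1−p) + (p+d)(1−p−d)]/26).

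For p = 0.10 and d = 0.20: s₀ = √(2 × 0.2 × 0.8/26) = 0.1109 and s₁ = √((0.09 + 0.21)/26) = 0.1074. Power = Φ[(0.20 − 0.988 × 0.1109)/0.1074] = Φ(0.84) = 0.800.

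The four values at p = 0.10 are 0.162, 0.509, 0.800 and 0.946, which match the plan. At p = 0.22 they are 0.162, 0.430, 0.716 and 0.906, which do not. The table therefore rests on 10% control.

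**Step 2: exact operating characteristics.** For x control and y experimental responders,

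z = [(y−x)/26] / √(q(1−q)·2/26), with q = (x+y)/52.

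Binomial probabilities were summed over all 27 × 27 outcomes with z > 0.988.

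| True difference | 0 | 0.10 | 0.20 | 0.30 |
|---|---|---|---|---|
| Plan, 16.24 | 0.16 | 0.51 | 0.80 | 0.95 |
| Exact, 10% control | 0.192 | 0.535 | 0.821 | 0.952 |
| Exact, 15% control | 0.176 | 0.483 | 0.762 | 0.925 |
| Exact, 22% control | 0.168 | 0.425 | 0.709 | 0.903 |

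Over 10-22% control the exact type I error runs from 0.168 to 0.192, with mean 0.177. Simulations of 1,000,000 runs agree: 0.1916 at 10%, 0.1765 at 15%, 0.1679 at 22%, and power 0.8213 for 10% versus 30%.

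**Step 3: source of the excess.** One responder against none gives z = 1.010, and three against one gives z = 1.041. Both pass. Under 10% in each arm their probabilities are 0.0121 and 0.0430, together 0.055 of the 0.192. Rounding between 0.16 and 0.162 is not the cause: the attainable z values on either side of the cut-off are 0.961 and 1.010, so z > 0.988 and z > 0.994 (level 0.16) give identical decisions.

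**Step 4: power away from 10%.** Exact power for a 20-point gain falls below 0.80 once the control rate passes about 11.7%. The control rate causes this, not the approximation: at 22% the approximation itself gives 0.716.

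**Step 5: intervals.** The plan's interval is p̂ ± 1.96·√(p̂(1−p̂)/26). Exact coverage was computed at n = 26 for true rates of 10-22% in steps of 0.01 percentage points.

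| Method | Coverage range | Mean | 2/26 | 0/26 |
|---|---|---|---|---|
| Normal approximation | about 80% to 95.0% | 90.0% | −2.6% to 17.9% | 0 to 0 |
| Wilson | 92.3% to 98.0% | 95.4% | 2.1% to 24.1% | 0 to 12.9% |
| Clopper-Pearson | 95.4% to 99.3% | 97.5% | 0.9% to 25.1% | 0 to 13.2% |

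The normal-approximation interval is below 95% at every rate on this grid and below 90% at 43% of them (93.2% at a true rate of 10%, 82.7% at 12%, 86.0% at 18%). Its lower limit is negative for 1, 2 or 3 responders. The chance of 0/26 is 0.9²⁶ = 6.5% at a true rate of 10% and 0.78²⁶ = 0.2% at 22%.

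**The case against.** The strongest reply is that nothing was miscalculated. All four entries follow from the method declared in 16.21 and again in 16.312. Naming a binomial model for the data does not promise exact enumeration. Section 16.22 points back to 16.21, which fixes the control rate at 10%, so the table's basis can be recovered. The excess error is 3.2 percentage points at 10% and 0.8 at 22%, in a screening design whose one-sided level is deliberately loose. Exact power at the design point is slightly better than stated. The inflation is also not general: exact error is 0.1597 at 26% control and 0.155 at 30%. The interval method is openly stated and plays no part in the 16.211 decision.

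Most of this stands, and it keeps the point minor. The sample size is sound, and repeating the control rate beside the table is an editorial improvement. The 22% row is a sensitivity case drawn from the plan's cited range, and the 90% mean coverage weights rates of 10-22% equally, which is a choice.

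Two things remain. Declaring an approximation makes 0.16 a legitimate nominal level, but not the actual probability of a positive declaration, which is what 16.24 says it reports. Stating the interval method does not give it 95% coverage.

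**Conclusion.** The concern holds and is minor. At the design control rate, the chance of recommending an ineffective regimen is 0.19, about 1 in 5, where the plan says 0.16, about 1 in 6. It stays above 0.16 across 10-22% control. The 80% power claim for 10% versus 30% stands, but the three power entries do not carry over to higher control rates. The per-arm 95% intervals cover about 90% on average over true rates of 10-22%.

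These results assume independent binomial arms, exactly 26 evaluable patients in each, the pooled z without continuity correction, and a true control rate within the range the plan cites. The corrections change the description and the reported precision, not the go/no-go decision.

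**What to change.** Keep z > 0.988 and 26 per arm.

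- **16.21, 16.211, 16.24 and 16.312:** call 0.16 the nominal (normal-approximation) level. Add that the exact one-sided type I error with 26 evaluable patients per arm is about 0.19 at the design control rate of 10%, falling to about 0.17 at 22%.
- **16.24:** label the table by control rate and use exact binomial values: 0.19, 0.53, 0.82 and 0.95 at 10%; as a sensitivity row, 0.17, 0.42, 0.71 and 0.90 at 22%.
- **16.312 and 16.34:** replace the normal-approximation intervals with Wilson intervals, whose mean coverage is closest to 95%, or with Clopper-Pearson if coverage of at least 95% is required. Use one method in both sections.

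This needs no extra patients and leaves the test and decision rule unchanged. The cost is less favourable stated figures: type I error of 0.17-0.19, and power of 0.71 for a 20-point gain at 22% control. Clopper-Pearson intervals are wider than Wilson.

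Moving the cut-off instead would cost power. The lowest attainable cut-off that holds exact error at or below 0.16 across 10-22% requires z above 1.041. It gives error of 0.135-0.151 but lowers exact power for 10% versus 30% from 0.821 to 0.793, just under the stated 80%.
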